The intervention is offered to females, aged 18 or 19, who self-identify as either Latina or African American, are visiting a participating reproductive health center, have been deemed appropriate for the study by clinic staff with regards to physical and mental health capacity, are not knowingly pregnant and not trying to get pregnant, have not participated in other Office of Adolescent Health-funded Teen Pregnancy Prevention (OAH TPP) programs, consent to participate in the study, and are willing to complete three- and nine-month follow-up questionnaires.

The treatment condition, *Plan A*, is 23-minute video intervention that promotes effective contraceptive use, use of dual methods of protection (condom use and prescription birth control use), and HIV/STI testing. The video aims to develop sexual health intentions, knowledge, and self-efficacy for communicating with providers about different contraceptive options that have been proven effective, such as LARC. The ultimate goal of the video is to influence viewers' uptake of LARC, reduce unprotected sexual activity, and increase receipt of STI testing.

The control (counterfactual) condition, *The Toxic Life Cycle of a Cigarette*, is a 17-minute video that details the negative effects that cigarettes have on the environment and on people who manufacture and use cigarettes. The informational video uses both narration and interviews to educate viewers on the dangers that cigarettes pose. The video includes no sexual or reproductive health content. The videos are delivered to study participants on laptops in a private room or area of participating reproductive health clinics.

- a. **Intervention condition:** The intervention or treatment condition is a 23-minute video called *Plan A*, which was developed by Sentient Research and is based on the entertainment-education model. Entertainment-education is a process of creating and implementing an entertainment program to increase knowledge, change attitudes, and change behaviors among a target audience regarding a social or health issue.² *Plan A* was developed specifically for an 18 to 19-year-old African American or Latina female audience, and delivers messages about the use of effective sexual protection and contraceptive options.

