Use of dual methods of protection during vaginal sex is constructed as a proportionate continuous measure – the proportion of number of times in the past three months a participant has used both a condom and prescription birth control out of the total number of times reported having vaginal sex in the past three months.^{13,14} Data used to assess the impact of the treatment (*Plan A*) on dual methods of protection are obtained from the following two items on the *Participant Questionnaire*, which is administered to both the treatment and control groups at baseline and three months post-baseline.

- *In the past three months, how many times have you had vaginal sex?*
- *Please think about how many times you said you had vaginal sex in question 20. Of the times you had vaginal sex, how many times would you say you used*

¹² See footnote **Error! Bookmark not defined.**

¹³ Participants are provided with a box directly above this question, which lists the specific types of prescription birth control to which we are referring. This list includes the following: *birth control pills; the patch (for example, Ortho Evra); the shot (for example, Depo Provera); the ring (for example, NuvaRing); the implant (for example, Implanon or Nexplanon); and IUD (for example, ParaGard, Skyla, or Mirena).*

¹⁴ See footnote **Error! Bookmark not defined.**

dual methods of protections – that is, how many times did you use both a condom and one of the listed methods of prescription birth control at the same time?

Only those participants who report having vaginal sex in the past three months at both baseline and three-month follow-up will be included in analysis. If an individual responds *No* to the question “*Have you ever had vaginal sex?*” or responds *No* to the question “*In the past 3 months, have you had vaginal sex, even once?*”, the individual will be excluded from analysis of this measure. Because of the fact that the mechanism defining the analytic sample for this research question is not random and there are theoretical reasons to believe that treatment assignment may affect inclusion (i.e., individuals who are offered the treatment may be more likely to abstain from sexual activity at follow-up and therefore excluded from the analytic sample) this constitutes an endogenous subgroup.¹⁵

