¹⁵Endogenous subgroups are groups of participants that are defined by an outcome measure. The expected balance in observed and unobserved characteristics between treatment and control participants that results from random assignment cannot be guaranteed in such subgroups and thus effect estimates may be subject to bias. Tests of baseline balance will be conducted; if we have reason to believe there is imbalance between treatment and comparison groups for this outcome, we will reduce this to an exploratory research question.

It should be noted that this measure will only be constructed for individuals who select either *None*, *Oral contraceptives*, *The patch*, *The shot/injection*, or *The ring* to the question “Which of the following birth control methods are you currently using?”. If an individual selects *The implant* or *IUD* to this question, the individual will be excluded from analysis of this measure. As such, the subgroup of participants in which we conduct this analysis will be considered an endogenous subgroup (i.e. not inclusive of our full analytic sample) because it is constructed based on a participant’s response to an outcome measure.¹⁶

Plan A will be considered to have a positive impact on use of other effective contraceptive methods if, as compared to participants who are assigned to the control group, a larger proportion of participants who are offered *Plan A* report using other effective contraceptive methods at the three-month follow-up and the difference between groups is statically significant.

- b. **Analytic sample:** In Central California, eight clinics have been recruited to participate in the study. As explained in the *Study Design* section, clinic-based study coordinators review administrative/clinic data for patients with appointments at the study clinics to identify potentially eligible participants.

Potential participants are eligible if they: 1) are female; 2) are between the ages of 18 and 19 years of age; 3) are Hispanic and/or Latina; 4) are not knowingly pregnant or trying to get pregnant; 5) consent/assent to participate; 6) did not enroll in the SpeakOut study between November 2016 to October 2018¹⁷; and 7) are deemed appropriate for the study with regards to physical and mental health by a clinician, clinic staff, or the study coordinator.

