We propose to assess baseline equivalence of the treatment and control groups according to a multi-step procedure. Baseline equivalence statistics will be produced for each analytic sample.³² Only participants who provide baseline data to an outcome measure will be included in the analytic sample for that same outcome measure; thus the analytic sample used for each research question may vary slightly because of the exclusion of non-responders. As required by the “Identifying Programs that Impact Teen Pregnancy, Sexually Transmitted Infections, and Associated Sexual Risk Behaviors” review protocol, we will report the adjusted means and p-values of the differences in the baseline variable of interest for the treatment and control groups.³³ We will also report the standardized mean difference of each baseline variable for the treatment and control groups. This last statistic is not required by the review protocol but it is more consistent with the literature on balance statistics.³⁴

²⁹ Age at screening is determined using the participant’s self-reported date of birth.

³⁰ At screening, participants are asked “What is your race and ethnicity?” and provided with a list of the following response options: *White; Black or African American; Hispanic, Latino, or Spanish origin; American Indian or Alaskan Native; Asian; Native Hawaiian/Other Pacific Islander; Unknown; or Some other race/ethnicity*. Participants can select more than one category and they can also specify some other race/ethnicity. To be eligible for the study, participants must select either *Black/African American* or *Hispanic, Latino, or Spanish origin*.

³¹ See footnote 30.

³² Due to item missing outcome data, we expect there may be slight differences in analytic samples for each research question.

³³ Goesling, B., & Trenholm, C. (2016). Identifying Programs that Impact Teen Pregnancy, Sexually Transmitted Infections, and Associated Sexual Risk Behaviors. Mathematica Policy Research.

³⁴ The literature on balance statistics argues that significance testing is inappropriate for this diagnostic task (Austin, 2007; Imai et al., 2008; Austin, 2009; Stuart, 2010). Hypothesis tests can be misleading diagnostic measures of baseline equivalence because they conflate balance with statistical power

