The resulting variable is a continuous proportion with values that range from 0 to 1, where 0 indicates that a person has used dual methods of protection 0% of the time during vaginal sex in the past three months, and 1 indicates the person has used dual methods of protection 100% of the time during vaginal sex in the past three months.

Note: The analytic sample will only include respondents who have three-month follow-up data and who indicate in their three-month follow-up questionnaire that they have had vaginal sex in the past three months. Persons who indicate they have never had vaginal sex or have not had vaginal sex in the past three months will be excluded from the construction of this measure.

Use of other effective contraceptive methods

The protective outcome is operationalized as a dichotomous variable indicating whether a person reports currently using prescription birth control methods beyond LARC or not currently using any prescription birth control methods.

*Participant
Questionnaire*

Three-month follow-up
(three months after enrollment)

The measure is calculated from the following item:

- Which of the following methods of prescription birth control are you currently using?
 - None: I am not currently using any of these methods
 - Oral contraceptives (for example, the pill)
 - The patch (for example, Ortho Evra)
 - The shot/injection (for example, Depo-Provera)
 - The ring (for example, NuvaRing)
 - The implant (for example, Implanon or Nexplanon)
 - IUD (for example, ParaGard, Skyla, or Mirena)

A person who selects either *Oral contraceptives*, *The patch*, *The shot/injection*, or *The ring* is given a value of 1 for the measure. A person who selects *None* is given a value of 0 for the measure.

The resulting variable is dichotomous with values 0 or 1, where 0 indicates a person who does not currently use any prescription birth control methods and 1 indicates a person who uses non-LARC prescription birth control methods.

Note: The analytic sample will only include respondents who have three-month follow-up data and who indicate in their three-month follow-up questionnaire that they are currently not using any birth control or using one of the non-LARC methods. Persons who indicate they use LARC methods will be excluded from the construction of this measure.

Table 2. Covariates included in primary and secondary impact analyses

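### Secondary outcome 2 is analysed only in women not using LARC at follow-up, so its positive-impact rule can register movement into LARC; separately, the dual-methods sample is stated two ways

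*SAP*

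**What the plan says.** **Other effective methods.** Section 4a (Secondary outcome measures, ii) codes pill, patch, shot or ring as 1 and none as 0. Implant and IUD users are left out: "to this question, the individual will be excluded from analysis of this measure". The Table 1 note in Appendix A applies this to the three-month answer: "Persons who indicate they use LARC methods will be excluded from the construction of this measure". The SAP calls the result an endogenous subgroup and, through footnote 16, applies footnote 15 to it. Footnote 15 warns that estimates may be biased, promises tests of baseline balance, and makes the question exploratory "if we have reason to believe there is imbalance between treatment and comparison groups for this outcome". Otherwise it stays secondary, and Plan A is credited with a positive impact if a larger proportion of women offered it "report using other effective contraceptive methods at the three-month follow-up and the difference between groups is statically significant".

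**The excluding variable.** Current LARC use at three months is primary outcome 1. Section 2 gives the goal of the video as to influence "uptake of LARC, reduce unprotected sexual activity, and increase receipt of STI testing".

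**Dual methods.** Section 4a (Secondary outcome measures, i) says that only participants who report "having vaginal sex in the past three months at both baseline and three-month follow-up will be included in analysis". The Table 1 note limits the sample to respondents with three-month data "who indicate in their three-month follow-up questionnaire that they have had vaginal sex in the past three months" and states no baseline condition.

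**The concern.** The analysis set for secondary outcome 2 is fixed after randomisation by a variable the treatment is meant to change. If Plan A works as intended on primary outcome 1, different women are removed from the two arms. The conditional proportion, other/(other + none), can then rise although no additional woman uses a pill, patch, shot or ring, and the stated rule would call that a positive impact on those methods. It can also fall because women move from a short-acting method to LARC while total method use is unchanged.

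The balance check looks at baseline characteristics. It may pass while the follow-up subsets still differ because of what treatment did between the two visits.

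The dual-methods issue is separate. A woman with vaginal sex in the past three months at follow-up but not at baseline is out under section 4a and is not excluded by Table 1, so two analysts could build different samples.

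**Working it through.** The SAP gives no method-use rates, so there is no plan figure to reproduce. What follows is an illustration.

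**Inputs**
- From the SAP: target of 1,770 (Study changes timeline, September 2017) and 1:1 allocation (section 3b), so 1,770/2 = 885 per arm. Two-sided p < .05 (section 4f), so 2.5% nominal in the positive direction.
- Assumed: control LARC/other/none = 15/50/35%; no attrition; no covariate adjustment.
- Assumed LARC gain: 4.3 points. This is 0.12 × √(0.15 × 0.85) = 0.0428, which reads the SAP's MDES of .12 as raw SD units of LARC use. The SAP names neither outcome nor scale for that MDES. On the Cox index (used in section 4d for baseline balance), ln odds = ln(0.15/0.85) + 0.12 × 1.65 gives 17.7%, a gain of 2.7 points.

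**Formula.** Let g be the gain and s the share of new LARC users who come from none.

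Control: 50/85 = 58.8%.

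Treatment: (50 − g(1 − s)) / (85 − g).

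SE = √(p_c(1 − p_c)/n_c + p_t(1 − p_t)/n_t), with n_c = 885 × 0.85 = 752 and n_t = 885 × 0.8072 = 714 at g = 4.28. The chance of a significant positive result is 1 − Φ(1.96 − difference/SE).

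**Results**

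| Gain (points) | Share from none | Treatment | Difference (points) | Chance of significant positive |
|---|---|---|---|---|
| 4.3 | 0% | 45.72/80.72 = 56.6% | −2.2 | below 1% |
| 4.3 | 30% | 58.2% | −0.6 | 1% |
| 4.3 | 41% (= 35/85) | 58.8% | 0 | 2.5% |
| 4.3 | 70% | 60.4% | +1.5 | 9% |
| 4.3 | 100% | 50/80.72 = 61.9% | +3.1 (SE 2.55, z = 1.22) | 23% |
| 2.7 | 100% | 50/82.3 = 60.8% | +1.9 (z = 0.76) | about 11.5% |

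**Same scenarios in the full sample, 4.3-point gain.** All from none: any listed method goes from 65% to 69.3%, and non-LARC use stays at 50%. All from other methods: any listed method stays at 65%, and non-LARC use goes from 50% to 45.7%. The three-way split tells these apart; the conditional proportion alone does not.

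**With adjustment.** The SAP plans to adjust for the baseline outcome. A simulation of OLS on arm, baseline other-method use and a missing-baseline dummy for baseline LARC users assumed that 30% or 60% of women simply keep their baseline category and the rest are redrawn from the same mix. At a 4.3-point gain all from none it gave about +1.9 to +2.9 points and a 15 to 22% chance. Adjustment shrinks the shift but does not remove it.

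**What the balance check covers.** Section 4d lists standardised differences and p-values without a cut-off. Its list of baseline outcome measures names only the three primary outcomes, although the section opens by promising each outcome variable. None of these statistics uses follow-up information.

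**Dual methods.** Section 4a requires vaginal sex at two time points; Table 1 mentions one. A woman with no vaginal sex in the three months before baseline has no defined baseline proportion, and the general text does not settle her case. Missing-data step 5 (section 4c.v) keeps women without a baseline outcome value by dummy-variable adjustment, whereas section 4d says "Only participants who provide baseline data to an outcome measure will be included in the analytic sample for that same outcome measure". No size can be given.

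**The case against.** The endogeneity is disclosed. The SAP names it, warns of bias and provides for demotion, and secondary outcomes sit outside the Benjamini-Hochberg family, so no primary conclusion depends on this one. That stands, and it limits the point to how the conditional result is labelled and read.

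A reader might infer from the all-from-none row that a misleading positive finding is likely. The documents do not support that: nothing says where new LARC users would come from, and a 30 to 70% share from none gives a small shift of either sign. Nor is 4.3 points the SAP's own effect size; it rests on one reading of an MDES given without a scale.

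A reader might also think that a numerical balance threshold would cure the problem. It would not, because a passed check says nothing about selection arising after baseline.

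The three-way split could be roughly rebuilt from primary outcome 1 and the conditional proportion. True, but the positive-impact rule does not ask anyone to do so.

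On dual methods, Table 1 can be read as giving a necessary condition to which section 4a adds another, so a sample built by section 4a breaks nothing in Table 1. That makes the conflict milder, but a table that defines the analytic sample should state the whole rule. It would also be tempting to demote the dual-methods question alongside the other. A mismatch in wording does not justify that.

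**Conclusion.** The concern holds in a limited form. Secondary outcome 2 conditions on a primary outcome measured at the same visit, and a baseline check cannot protect against the resulting selection. A significant rise in the conditional proportion is therefore not, taken alone, evidence that Plan A increased use of other methods.

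The size depends on assumptions the SAP neither supplies nor rules out. Under those used here the shift ranges from −2.2 to +3.1 points at a 4.3-point LARC gain and is near zero when new LARC users come from the two groups in proportion. No scenario shown is significant in expectation. The primary analyses are unaffected.

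The dual-methods sample is a separate drafting inconsistency of unknown size.

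**What to change.** 1. **Other effective methods.** Report the LARC/other/none split by arm among all three-month respondents. Add a full-sample comparison of any listed prescription method against none and, if wanted, non-LARC method use with LARC users coded 0. Do not declare a positive impact on other methods from the conditional proportion alone, and label that analysis exploratory or descriptive whatever the balance check shows.

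2. **Dual methods.** State one inclusion rule in section 4a and Table 1, and say how women with no defined baseline value are handled, so that missing-data step 5 and section 4d agree.

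The cost is SAP wording and one table from a questionnaire item already collected. There are two drawbacks. Any listed method includes LARC, so that comparison must be read with primary outcome 1 and does not replace the conditional measure. The conditional version of secondary outcome 2 also loses its secondary status. The changes should be made before three-month outcomes are compared by arm.

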- ii. **Identify and flag invalid responses:** The second step in the data screening process is to inspect the data for instances in which responses are invalid because they are outside of a pre-determined range of plausible or acceptable values. Each questionnaire type (e.g., baseline, three-month follow-up) has a codebook, which is prepared by a PRG staff, that contains variable names, valid variable values or ranges of values, and when applicable value labels.²² Referring to the codebook, a senior or lead research analyst performs diagnostics in STATA to ensure that responses to all analytic measures are valid (i.e., data are within ranges specified in the codebook). A data analyst inspects the data using two commands in STATA. First the analyst uses the command *sum variable_name*, which provides summary statistics (mean, minimum, maximum, standard deviation) for all numeric variables. The analyst checks that the minimum and maximum values are valid. If this command reveals there are values out of range, the analyst then inspects the data using the command, *tab variable_name, missing*, which provides a frequency table of all values (including missing values) so the analyst can identify and flag all values that are out of range as invalid and recode these values to missing (code as ".i").

Data that are recoded to missing are treated according to our missing data approach. Briefly, our benchmark approach is to adjust missing baseline data and include in analysis; we exclude observations with missing outcome data from analysis.

²⁰ A note on missing values: STATA provides a series of missing value codes that allow us to "flag" missing data according to why they are missing. Data that are missing due to unit nonresponse (a questionnaire was not completed) are coded using the "system missing" value (.). All other types of missing data are coded using "extended missing" values (e.g., ".a", ".b").

²¹ See *Comparing and Evaluating Youth Substance Use Estimates from the NSDUH and Other Surveys* retrieved February 27, 2018 from <https://www.samhsa.gov/data/sites/default/files/NSDUH-M9-Youth-2012/NSDUH-M9-Youth-2012.pdf>.

²² Regardless as to whether data are nominal, ordinal, or continuous, all response options are coded in STATA as numeric values; values are labeled according to corresponding category names when data are nominal or ordinal. As an example, the variable gender is a nominal variable; however, it is treated as a dummy variable where females are coded as "1" and males are coded as "0". The only acceptable values for this variable then are 0 and 1; any other values are out of range.

iii. **Identify and flag outliers:** The third step is to identify and flag severe outliers. Outliers (operationally defined below) are values that are extreme compared to other observations but are not plainly invalid. In the data cleaning process, we inspect outliers so that we can try to ascertain whether they are in fact true (or plausible) values or potentially a result of measurement error. The only variables for which we inspect outliers are those used in the construction of our outcome variables (times having vaginal sex, times having vaginal sex without a condom, times having oral sex, times having oral sex without a condom, times having anal sex, times having anal sex without a condom) because they have no upper limit (all other variables used in analysis are either categorical or have predicated upper and lower bounds). Our approach to identifying and flagging outliers is as follows.²³

- First, in STATA we use the *lv* (letter-value display) command to identify severe outliers. We define values as severe outliers according to their relation to the interquartile range (IQR). Severe outliers are defined as values outside of the *outer fences* of the population distribution.
 - $IQR = Q3(3^{\text{rd}} \text{ quartile or } 75^{\text{th}} \text{ percentile}) - Q1(1^{\text{st}} \text{ quartile or } 25^{\text{th}} \text{ percentile})$
 - Upper outer fence: $Q3 + 3 * IQ$
 - Lower outer fence: $Q1 - 3 * IQ$
- Second, we create an outlier indicator variable, where observations deemed severe outliers are coded as 1, all others are coded as 0.

Our benchmark analytic approach is to include data flagged as outliers in analysis, because we do not know for certain whether the values are true or invalid. However, we also run sensitivity analyses that exclude these data and report substantive differences in the results section of the report.

iv. **Identify and flag inconsistencies in reporting of sexual behaviors:** The fourth step in the data review process is to inspect the data and identify inconsistencies in sexual behavior outcome data. With repeated measures of sexual behaviors, two primary types of inconsistencies may occur – internal inconsistencies and over-time inconsistencies.²⁴ Internal inconsistencies refer to discrepancies in responses (to related questions) in the same survey administration. For instance, a respondent might say that she has not had sex in the past three months, but then indicates that she used condoms three of the times she had sex in the past three months. Over-time inconsistencies refer to instances in which lifetime reported behaviors decline or are completely recanted over time. For example, at baseline a respondent might say that she has had vaginal sex in her life, but on a subsequent administration of the survey she says she has never had vaginal sex.

In order to minimize internal inconsistencies in our primary and secondary outcomes, we built skip patterns into the online questionnaire – if participants indicate they have not had a particular type of sex in the past 3 months they are skipped out of more specific questions related to that type of sex. In addition, participants are precluded from indicating they had a particular type of sex without a condom more times than they said

²³ Rules for identifying outliers are informed by the following: Hamilton, Lawrence C. 2006. *Statistics with STATA: Updated for Version 9 and NIST/SEMATECH e-Handbook of Statistical Methods*, <http://www.itl.nist.gov/div898/handbook/>.

²⁴ Inconsistencies can occur for a number of reasons including social desirability bias and memory or recall issues on the part of the respondent and misunderstanding on the part of either the respondent or interviewer (Alexander et al 1993; Clarke, Fiebig, and Gerdtam 2008; Del Boca and Noll 2000; Harris et al 2008; Schroeder et al 2003; Schwarz and Oyserman 2001). These issues are especially common in self-reports of sexual behaviors where questions are of a sensitive nature and often respondents are asked to indicate the frequency and/or recency of behaviors over differing lengths of time (e.g., 30 days, 3 months, 6 months).

they had that type of sex. Because of this, no internal inconsistencies can exist in our primary and secondary outcome measures.²⁵

To address over-time inconsistencies, a research analyst examines all variables that are used to construct primary and secondary outcome measures, as well as any variables that may be used to logically impute values for primary and secondary outcome measures. If over-time inconsistencies are identified, both the baseline and follow-up values are flagged as inconsistent over time and recoded to missing (coded as “.k.”). Data that are recoded to missing are treated according to our missing data approach. Briefly, our benchmark approach is to adjust missing baseline data and include in analysis; we exclude observations with missing outcome data from analysis.

- v. **Missing data approach:** Assuming that our study design and procedures are sound, missing data pose perhaps the greatest threat to the internal validity of our RCT study and the ITT framework (Puma et al. 2009; Moher et al., 2010).²⁶ Randomization at the point of offer allows us to make causal statements about the effect of that offer because treatment and comparison samples are equal in expectation. For ITT framework to remain internally valid, however, the treatment and comparison groups must remain equal in expectation at the point of analysis. When the analytic sample is diminished by attrition or non-response, non-random differences (i.e., self-selecting) between the treatment and comparison groups may be introduced into the sample and estimates of program impacts may become biased. Although there is no consensus on how to resolve this, practical guidance on how to address and mitigate the problems associated with missing data have been published in education (Puma et al., 2009).

Our six-step decision processes for addressing this problem, as detailed below, are informed by this guidance. These steps articulate how we will deal with missing outcome or covariate data (that is variables outlined in the *Model specification and covariates* section and are necessary for the estimation of impacts). The benchmark approach that we have selected aims to mitigate the introduction of bias into our impact estimates, provide good estimates of uncertainty, and maximize the use of available data by adjusting missing baseline/covariate data. To test the robustness of this approach, and to verify these findings, we will report comparative findings using sensitivity analyses that also employ an alternative method which includes no adjustment (as outlined in step 6).

1. Using data cleaning procedures outlined in the *Data cleaning* section, identify inconsistent, outlying, unreliable, and invalid data in any analytic (i.e., outcome,

²⁵ In rare instances, paper-based questionnaires are completed by participants. This may occur if the study coordinator or research assistant is unable to open the online questionnaire because of network connection issues, or if the participant cannot be reached for an online administration and is instead mailed a paper questionnaire. Paper-based questionnaires include the same skip patterns as online questionnaires; however, unlike the online questionnaire where participants are skipped out of subsequent questions based on their response to previous questions and cannot report inconsistent times having different types of sex, it is possible for participants to provide responses to questions that they should not have answered or that do not make sense given their responses to previous questions. If and when such inconsistencies are observed in data originating from paper-based questionnaires, the participant's responses to the two or more items where inconsistencies are noted are recoded to system missing and will not be used in our primary and secondary outcome analysis.

²⁶ Puma, M.J., Olsen, R.B., Bell, S.H., Price, C. (2009). What to Do When Data Are Missing in Group Randomized Controlled Trials. (NCEE 2009-0049). Washington, DC: National Center for Education Evaluation and Regional Assistance, Institute of Education Sciences, U.S. Department of Education. Moher, D. et al. (2010). CONSORT 2010 Explanation and Elaboration: Updated Guidelines for Reporting Parallel Group Randomised Trials. *BMJ* 2010;340:c869.

baseline, or covariate) variables, recode inconsistent and invalid data as missing, and flag unreliable and outlier data for analysis.²⁷

2. Report prevalence of unit and item missingness (which result from nonresponse) as well as inconsistent, unreliable, and invalid data for both treatment and control samples.²⁸
 3. Determine if logical imputations are possible for any analytic variables, other than outcome variables, that may have missing values (due to nonresponse) and logically impute where this is the case. We will not logically impute where the missing values are previously inconsistent, unreliable, or invalid.
 4. Determine if any individuals who are in the randomized sample have no data at all (i.e., unit missing) at baseline and at the three-month follow-up time point. If this is the case, our proposed benchmark approach is to use case deletion, as we feel it is the most straightforward and prudent approach for missing follow-up data recommended in Puma et al. (2009). These cases will be deleted from the analytic sample and attrition statistics will be reported.
 5. Determine if any individuals who are in the randomized sample (for each outcome) are missing baseline covariates or the baseline measure of the outcome variable. If this is the case, our proposed benchmark approach is to use dummy variable adjustment procedures, as we feel it is the most straightforward and prudent approach for missing baseline/covariate data recommended in Puma et al. (2009).
 6. Conduct sensitivity analyses by estimating results with missing baseline data excluded from the analysis (i.e., use case-wise deletion for all cases with missing baseline and outcome data). In an appendix, we will report our benchmark results next to the sensitivity analysis results to verify findings.
- d. **Assessment of baseline equivalence:** Baseline equivalence will be reported for all baseline measures of each outcome variable as well as relevant demographic and sexual behavioral measures. We first list and describe the measures we will use to examine the equivalence of our treatment and control group at baseline. After we identify the measures, we provide details on the diagnostic methods that we will use to assess any baseline difference that may exist between the treatment and control groups in the measures outlined below.

Demographic and Sexual Behavior Measures

Baseline equivalence will be assessed for four demographic variables and one baseline measure of sexual behavior (identified below). Each of the variables are constructed from participant self-responses to questions in either the *Eligibility Screening Form* or VHS baseline *Participant Questionnaire*. For the race variables, categorical responses to a single question are used to create multiple dichotomous variables. The sexual behavioral variable is constructed from participants' responses to three questions in the baseline *Participant Questionnaire*. We provide details on

²⁷ We will code missing responses with a unique missing code that identifies or flags these missing values according to the reason they are missing (i.e., nonresponse, invalid, inconsistent). Unreliable data are not recoded to missing, rather cases deemed unreliable are coded as 1 in an indicator variable, treated as unit missing, and excluded from analysis. See the *Data cleaning* section or Table 3 in Appendix A for details on how missing data are coded.

²⁸ For item missing values, we will only report prevalence of missing and inconsistent data for variables that are included in our model specifications and could therefore influence the constitution of the analytic sample.

variable coding below; details on variable construction can be found in Table 2 in Appendix A.

Demographic:

- Age at screening (continuous; range 18-19)²⁹
- Identify as Black/African American at screening (0 = identify as another race/do not identify race; 1 = identify as Black/African American)³⁰
- Identify as Hispanic, Latino, or of Spanish origin at screening (0=do not identify as Hispanic, Latino, or of Spanish origin; 1= identify as Hispanic, Latino, or of Spanish origin)³¹
- Completed high school (0 = has not completed high school; 1= has completed high school)

Sexual Behavior:

- Ever had sex (0=never had vaginal, anal, or oral sex; 1=has had vaginal, anal, and/or oral sex in lifetime);

Baseline Outcome Measures

In addition to the demographic and sexual behavior measures, we will assess baseline equivalency of the baseline observations of the outcome measures. We provide details on variable coding below; details on variable construction can be found in Table 2 in Appendix A.

- *Times having sex without condom in the past 3 months* at baseline (continuous; values range 0 to k , where 0= has had sex without condoms 0 times in past 3 months and k = number of times having sex without condoms in past 3 months)
- *Current LARC use* at baseline (0= not currently using a LARC; 1= currently using a LARC)
- *STI Testing in the past 3 months* at baseline (0=not tested for STIs/STDs in past 3 months; 1= tested for STIs/STDs in past 3 months)

Balance Assessment Methods

We propose to assess baseline equivalence of the treatment and control groups according to a multi-step procedure. Baseline equivalence statistics will be produced for each analytic sample.³² Only participants who provide baseline data to an outcome measure will be included in the analytic sample for that same outcome measure; thus the analytic sample used for each research question may vary slightly because of the exclusion of non-responders. As required by the “Identifying Programs that Impact Teen Pregnancy, Sexually Transmitted Infections, and Associated Sexual Risk Behaviors” review protocol, we will report the adjusted means and p-values of the differences in the baseline variable of interest for the treatment and control groups.³³ We will also report the standardized mean difference of each baseline variable for the treatment and control groups. This last statistic is not required by the review protocol but it is more consistent with the literature on balance statistics.³⁴

²⁹ Age at screening is determined using the participant’s self-reported date of birth.

³⁰ At screening, participants are asked “What is your race and ethnicity?” and provided with a list of the following response options: *White; Black or African American; Hispanic, Latino, or Spanish origin; American Indian or Alaskan Native; Asian; Native Hawaiian/Other Pacific Islander; Unknown; or Some other race/ethnicity*. Participants can select more than one category and they can also specify some other race/ethnicity. To be eligible for the study, participants must select either *Black/African American* or *Hispanic, Latino, or Spanish origin*.

³¹ See footnote 30.

³² Due to item missing outcome data, we expect there may be slight differences in analytic samples for each research question.

³³ Goesling, B., & Trenholm, C. (2016). Identifying Programs that Impact Teen Pregnancy, Sexually Transmitted Infections, and Associated Sexual Risk Behaviors. Mathematica Policy Research.

³⁴ The literature on balance statistics argues that significance testing is inappropriate for this diagnostic task (Austin, 2007; Imai et al., 2008; Austin, 2009; Stuart, 2010). Hypothesis tests can be misleading diagnostic measures of baseline equivalence because they conflate balance with statistical power

